### 14.3 Clinical Laboratory Variables

Due to COVID-19 PHE related disruptions, it is possible that some test results may be collected from a local laboratory. Local laboratory results and the associated normal ranges will be converted to SI units; local laboratory results, in SI units, will then be normalized to central lab ranges to be included in summary data analysis together with the central laboratory results. The normalization will be performed using the following scale transformation equation:

$$s = L_s + (x - L_x) \frac{U_s - L_s}{U_x - L_x}$$

where s is the normalized individual laboratory value to be used for summary; x is the original value from the local lab;  $L_x$  and  $U_x$  are the lower and upper limits from the local lab;  $L_s$  and  $U_s$  are the lower and upper limits from the central lab.

For labs with only a single upper (or lower) limit, the following scale transformation equation will be used:

$$s = x \frac{U_s}{U_x}$$

where s is the normalized individual laboratory value to be used for summary; x is the original value from the local lab;  $U_s$  is the upper (or lower) limit from the central lab;  $U_x$  is the upper (or lower) limit from the local laboratory. Local laboratory results and normalized results will be included in data listings. Only central lab and normalized local lab results will be used for summary of change from baseline, shift, and potentially clinically important (PCI) analyses.

Clinical laboratory assessments are performed at Baseline, Week 12, Week 52, Week 104 and Week 130/EOT.

- Clinical chemistry serum tests include the following:
  - Sodium (Na), potassium (K), chloride (Cl), phosphorus (P), calcium (Ca), carbon dioxide (CO2), blood urea nitrogen (BUN), creatinine (CR), uric acid
  - Alanine aminotransferase (ALT), aspartate aminotransferase (AST), gamma-glutamyl transpeptidase (GGT), alkaline phosphatase (ALP), total bilirubin (TBIL), lactate dehydrogenase (LDH)
  - Glucose
  - Albumin (ALB), total protein
- Pregnancy test
  - A serum pregnancy test will be performed at all designated visits for subjects of childbearing potential
- Hematology tests include the following:
  - Complete blood count (CBC) including:
    - White blood cell (WBC) count
    - Complete differential (relative and absolute)
    - Hematocrit (Hct), hemoglobin, red blood cells (RBC), platelets
    - Reticulocyte count
- Urinalysis tests include the following:
  - Blood, RBCs, WBCs, protein, glucose, ketones, specific gravity, pH

Clinical laboratory values (in Système International [SI] units) and the change from Baseline values will be summarized at each post-Baseline visit using descriptive statistics. The overall minimum, maximum as well as the last post-Baseline observed and change from Baseline values will also be summarized. For urinalysis with categorical results, the number and percentage of subjects will be tabulated by category at Baseline and each post-Baseline visit, and the denominator is the number of subjects with non-missing values for the given parameter and visit.

Laboratory values will also be summarized in shift tables to determine the number and percentage of subjects with values classified as below, within, and above normal ranges at each post-Baseline visit relative to the same classification at the Baseline visit. For the by-visit shift summary, the denominator is the number of subjects with non-missing values at Baseline and the

given visit for the given parameter. For the shift to the overall post-Baseline minimum or maximum, all post-Baseline values will be considered, including unscheduled and out of window values and the denominator is the number of subjects with non-missing Baseline value and at least 1 post-Baseline value for the given parameter.

Clinical laboratory values are potentially clinically important (PCI) if they meet either the low or high PCI criteria listed in [Tables 5](#) and [6](#). The number and percentage of subjects with post-Baseline PCI values for each of the categories in Table 5 and 6 will be summarized for selected parameters. For the overall post-Baseline summaries of PCI values, all post-Baseline values will be considered, including unscheduled and out of window values. Subjects with multiple PCI values for a given parameter will be counted only once for that parameter. For the overall post-Baseline summary, the numerator of the percentage is the number of subjects with at least 1 post-Baseline PCI laboratory value for the given parameter, and the denominator is the number of subjects with at least 1 post-Baseline laboratory value for the given parameter.

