### **14.1 Primary Safety Endpoints**

The primary safety endpoints are:

- Treatment-emergent adverse events (TEAEs)
- Serious adverse events (SAEs)
- Withdrawals due to adverse events (AEs)
- Potentially clinically important changes in other safety assessments

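### The two-limit rescaling of local laboratory results changes their multiple of ULN, so a ULN-based PCI flag near the cut-off can be lost or gained

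*SAP*

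**What the plan says.** SAP Section 14.3 allows for local laboratory data as a pandemic contingency: "Due to COVID-19 PHE related disruptions, it is possible that some test results may be collected from a local laboratory". Such results are converted to SI units and normalised to the central range by a linear formula that uses both limits of both laboratories. A second, purely proportional formula is kept for a narrower case: "For labs with only a single upper (or lower) limit, the following scale transformation equation will be used".

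The normalised values feed the analyses without exception: "Only central lab and normalized local lab results will be used for summary of change from baseline, shift, and potentially clinically important (PCI) analyses". The original values are retained only for display: "Local laboratory results and normalized results will be included in data listings".

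The same section derives PCI status from the latest version of the central laboratory's main reference range. Table 5 sets the high criterion as a multiple of ULN for seven analytes: at least 3 for ALT, AST, LDH, ALP and GGT, at least 1.5 for total bilirubin, and above 1.5 for serum creatinine. Counts of subjects with PCI values "will be summarized for selected parameters". Section 14.1 lists "Potentially clinically important changes in other safety assessments" among the four primary safety endpoints.

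**The concern.** A criterion of 3 × ULN asks how far a result lies above the upper limit, in units of that limit. It makes no use of a lower limit. The two-limit formula measures distance above ULN in units of the width of the reference range, so the lower limits of both laboratories enter the answer. A local ALT that meets the criterion against its own laboratory's ULN can fall short after rescaling, and one that does not meet it can be flagged.

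At stake are the PCI counts and the PCI listing for liver enzymes, bilirubin and creatinine. A subject needs only one post-Baseline PCI value for a parameter to be counted in the overall summary, so one altered result can change that subject's status.

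**Working it through.** **Inputs from SAP Section 14.3**

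- Two-limit formula: s = Ls + (x − Lx)(Us − Ls)/(Ux − Lx), where x is the local result, Lx and Ux are the local limits, and Ls and Us are the central limits.
- Single-limit formula: s = x·Us/Ux.
- The normalised s is judged against a multiple of the central ULN, Us.
- Cut-offs from Table 5: 3 (five analytes) and 1.5 (two analytes).

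The documents give no reference ranges and no count of local samples. Every range and ratio below is an illustrative assumption.

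**Algebra.** Put x = k·Ux, rx = Lx/Ux and rs = Ls/Us. Subtracting Us from both sides of the two-limit formula gives s − Us = (k − 1)·Ux·(Us − Ls)/(Ux − Lx). Dividing by Us:

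s/Us = 1 + (k − 1)(1 − rs)/(1 − rx)

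For k above 1 this equals k only if rx = rs. The local multiple needed to reach a cut-off c after rescaling is 1 + (c − 1)(1 − rx)/(1 − rs). Under the single-limit formula, s/Us = x/Ux = k always.

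**What a result exactly at the cut-off becomes**

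| rx (local) | rs (central) | 3.0 × ULN becomes | 1.5 × ULN becomes |
|---|---|---|---|
| 0.10 | 0.30 | 1 + 2(0.70/0.90) = 2.56 | 1 + 0.5(0.70/0.90) = 1.39 |
| 0.30 | 0.10 | 1 + 2(0.90/0.70) = 3.57 | 1 + 0.5(0.90/0.70) = 1.64 |
| 0.25 | 0.30 | 1 + 2(0.70/0.75) = 2.87 | 1 + 0.5(0.70/0.75) = 1.47 |
| 0.30 | 0.25 | 1 + 2(0.75/0.70) = 3.14 | 1 + 0.5(0.75/0.70) = 1.54 |
| equal | equal | 3.00 | 1.50 |

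The first two rows are the extremes when each ratio lies between 0.1 and 0.3. The next two are the extremes within that span when the ratios differ by at most 0.05.

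**Worked results**

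- *Flag lost.* Local range 5–40, central 10–40, ALT 130. Locally 130/40 = 3.25. Normalised: 10 + 125 × 30/35 = 117.1, and 117.1/40 = 2.93. The local multiple needed is 1 + 2(0.875/0.75) = 3.33, so local values from 3.00 to just under 3.33 × ULN lose the flag.
- *Flag gained.* Local 10–40, central 10–50, ALT 116. Locally 116/40 = 2.90. Normalised: 10 + 106 × 40/30 = 151.3, and 151.3/50 = 3.03. The single-limit formula gives 116 × 50/40 = 145, and 145/50 = 2.90.
- *No change.* Local 8–40, central 10–50, ALT 120. Normalised: 10 + 112 × 40/32 = 150, and 150/50 = 3.00. The lower limits differ but the ratios are the same.
- *At the 1.5 cut-off, with narrower ranges.* Local 40–80, central 50–80, result 122. Locally 122/80 = 1.53. Normalised: 50 + 82 × 30/40 = 111.5, and 111.5/80 = 1.39, so the flag is lost.

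**Shift tables.** The formula sends Lx to Ls and Ux to Us and is increasing, so the low, normal and high classes do not change.

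**The case against.** The strongest reply is that the SAP has made a coherent choice. It places local results on one central scale and judges s against the central ULN, and nothing in the documents says that the local multiple must survive. A flag changes only if a local sample was used, two limits were available from both laboratories, their ratios differed and the result lay near the cut-off. The documents establish none of these. If an enzyme's ranges have only an upper limit, the single-limit formula already applies and there is no problem for that analyte. Original values are listed, so an altered flag can be traced, and no hypothesis is tested.

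Most of this limits the reach of the point, and those limits stand. It does not justify the rule. Prespecifying the scale does not explain why lower limits should decide whether a result reaches a multiple of ULN, and the error is not conservative because it runs both ways. Listing the original values does not correct the counts.

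It is also said that the plan leaves no real choice of formula when only one laboratory reports a lower limit, because the two-limit formula cannot then be computed. That is the natural reading, but the SAP does not state it. A missing lower limit entered as zero would make the formula computable: local 0–40, central 10–40, result 120 gives 10 + 120 × 30/40 = 100, or 2.50 × ULN instead of 3.00.

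Finally, normalisation also moves results relative to Table 5's fixed cut-offs, such as those for sodium or potassium, and the change proposed here does not address them. That is true. Those criteria are absolute concentrations and raise a separate question.

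**Conclusion.** The concern holds, as a minor one. The two-limit formula does not preserve the quantity on which seven Table 5 criteria are defined, and the algebra does not depend on any assumed range. The size does. With lower/upper ratios within 0.05 of each other in the span 0.1 to 0.3, a local 3.0 × ULN is analysed as 2.87 to 3.14 and a local 1.5 × ULN as 1.47 to 1.54, so only results close to the cut-off are exposed. Wider differences between laboratories widen that band.

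The effect on reported PCI percentages cannot be computed, because the number of local samples is unknown, and it may be nil. For scale only: with the planned 153 subjects all contributing a post-Baseline value, one subject whose status changes moves an overall percentage by 1/153, about 0.65 percentage points. Means and changes from Baseline on the normalised scale are not in dispute.

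**What to change.** Add one sentence to SAP Section 14.3: for PCI criteria expressed as a multiple of ULN, local results are normalised by s = x·Us/Ux (equivalently, x/Ux is compared with the cut-off), including when only one laboratory reports a lower limit. Keep the two-limit values for means, change from Baseline and shift tables. The rule that PCI status is judged against the latest central range can stay as written.

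Add a footnote to the PCI table stating that a local sample for these seven analytes may carry one value in the PCI output and another in the change-from-Baseline output. That is the one real drawback: a subject could be flagged at 3 × ULN while the maximum shown elsewhere is slightly below it, or the reverse.

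The cost is the sentence, the footnote and a small programming change. No new data are needed, since the local results and upper limits are already required by the existing formulas.

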**Table 5 Criteria for Potentially Clinically Important Laboratory Values – Hematology and Chemistry**

Analyte	Conventional Unit	Low PCI Criteria	High PCI Criteria	SI Unit	Low PCI Criteria	High PCI Criteria
Hematology (whole blood)						
Hemoglobin (female)	g/dL	<10	>17	g/L	<100	>170
Hematocrit (female)	%	<30	>50	L/L	<0.3	>0.5
Leukocyte (White Blood Cell Count)	x 10  /uL	≤2.8	≥15	x 10  /L	≤2.8	≥15
Neutrophils	x 10  /uL	≤1.5	No upper limit	x 10  /L	≤1.5	No upper limit
Platelet Count	x 10  /uL	≤75	≥700	x 10  /L	≤75	≥700
Chemistry (serum or plasma)						
ALT	U/L	No lower limit	≥3 X ULN	U/L	No lower limit	≥3 X ULN
AST	U/L	No lower limit	≥3 X ULN	U/L	No lower limit	≥3 X ULN
Total Bilirubin	mg/dL	No lower limit	≥1.5 ULN	umol/L	No lower limit	≥1.5 ULN
BUN	mg/dL	No lower limit	≥30.0	mmol/L	No lower limit	≥10.71
Sodium	mEq/L	≤125	≥155	mmol/L	≤125	≥155
Potassium	mEq/L	≤3.0	≥5.5	mmol/L	≤3.0	≥5.5
Calcium, total	mg/dL	<8.0	>11.0	mmol/L	<2.0	>2.75
Lactate Dehydrogenase (LDH)	U/L	No lower limit	≥3 X ULN	U/L	No lower limit	≥3 X ULN
Alkaline Phosphatase	U/L	No lower limit	≥3 X ULN	U/L	No lower limit	≥3 X ULN
Uric acid (female)	mg/dL	No lower limit	≥8.5	umol/L	No lower limit	≥505.75
Albumin	g/dL	≤2.6	≥6.0	g/L	≤26	≥60
Total Protein	g/dL	≤5.0	≥10.0	g/L	≤50	≥100
Chloride	mEq/L	≤85	≥120	mmol/L	≤85	≥120
Glucose (random)	mg/dL	≤45.1	≥200.0	mmol/L	≤2.48	≥11
Serum Creatinine	mg/dL	Not Applicable	>1.5 ULN	umol/L	Not Applicable	>1.5 ULN
Gamma-Glutamyl Transferase (GGT)	U/L	Not Applicable	≥3 ULN	U/L	Not Applicable	≥3 ULN

**Table 6 Criteria for Potentially Clinically Important Laboratory Values - Urinalysis**

Urinalysis (qualitative dipstick)	Low PCI Criteria	High PCI Criteria
Blood (occult blood)	Not Applicable	$\geq$ Moderate
Protein	Not Applicable	$\geq 100$ mg/dL
Glucose	Not Applicable	$\geq 500$ mg/dL

Clinical laboratory data will be displayed in data listings with date and study day of collection. All units will be displayed according to SI conventions for units. Out of range values will be flagged in the data listings (i.e., 'L' or 'H'). A separate listing will be provided for a subset of the chemistry, hematology, and urinalysis analytes with values classified as PCI.

At the initiation of the study, the main reference ranges (the reference ranges provided by the central laboratory validated for use for the general population) were used for the purpose of flagging abnormal laboratory values for the investigator to assess clinical significance. During the study, at the request of a leading investigator an alternative set of reference ranges, more specific to patients with Rett syndrome rather than to the general population, was used for the purpose of flagging abnormal lab values for the investigator to assess clinical significance.

All analysis will be done using the main reference ranges, not the alternative ranges. During the course of the study the main reference ranges were updated by the central laboratory. The latest version of the reference ranges provided by the central laboratory will be used for all analysis; PCI status and categorical labs (Low, Normal, High) and shifts will be derived from the latest version of the main reference range. Both of the reference ranges (main and alternative) and the corresponding categorical assessment will be listed.

The pregnancy results (positive or negative) will be presented in a listing.

#### **14.4 Vital Signs**

Vital signs will be collected throughout the study; height and weight will be measured at Baseline and Weeks 12, 52, 104, and 130/EOT. Observed vital signs including weight and BMI and the changes from Baseline at each post-Baseline visit will be summarized using descriptive statistics.

Vital sign values will be considered PCI if they meet the criteria listed in [Table 7](#). The number and percentage of subjects with post-Baseline vital signs that are PCI will be summarized at each post-Baseline visit and for overall post-Baseline. For the overall post-Baseline summaries, all post-Baseline values will be considered, including unscheduled and out of window values. Subjects with multiple PCI values for a given parameter will be counted only once for that parameter. For the by-visit summary, the numerator for the percentage is the number of subjects

with a post-Baseline PCI vital sign for the given parameter and visit, and the denominator is the number of subjects with non-missing values for the given parameter and visit. For the overall post-Baseline summary, the numerator for the percentage is the number of subjects with at least 1 post-Baseline PCI vital sign for the given parameter, and the denominator is the number of subjects with at least 1 post-Baseline vital sign for the given parameter. A listing of overall and of subjects with any PCI vital sign values will be provided.

**Table 7 Criteria for Potentially Clinically Important Vital Signs**

Vital Sign Parameter	Unit	Criteria			
		Observed Value	And/Or	Change Relative to Baseline	Change from Supine to Standing
Systolic blood pressure (supine or sitting)	mmHg	≥180	And	Increase of ≥20	-
		≤90	And	Decrease of ≥20	-
Diastolic blood pressure (supine or sitting)	mmHg	≥105	And	Increase of ≥15	-
		≤50	And	Decrease of ≥15	-
Pulse (supine or sitting)	bpm	≥120	And	Increase of ≥15	-
		≤50	And	Decrease of ≥15	-
Weight	kg	Not Applicable		Increase of ≥7%	-
				Decrease of ≥7%	-

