## **8. DEMOGRAPHICS AND BASELINE CHARACTERISTICS**

Demographics and baseline characteristics will be summarized for the Safety Analysis Set using descriptive statistics, using the baseline for this study. Variables include, but are not limited to, age, age group (5-10 years old, 11-15 years old, and  $\geq$  16 years old), race, ethnicity, height, weight, BMI, Baseline RSBQ total score, Baseline RSBQ severity (< 35 total score and  $\geq$  35 total score), and Baseline CGI-S score.

Race will also be categorized by White vs. Non-White. The reported age reflects a subject's age at the informed consent date of this study. Baseline characteristics for subjects in ACP-2566-005 will also be summarized using the baseline of the antecedent DB study ACP-2566-003 separately.

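### SAP Table 7 counts a blood pressure rise as PCI only if it reaches 180 mmHg systolic or 105 mmHg diastolic at any age, so its high-side rows are likely to be nearly empty for subjects aged 5-15

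*SAP*

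**What the plan says.** SAP Section 14.1 lists "Potentially clinically important changes in other safety assessments" among the primary safety endpoints. For vital signs, Section 14.4 defines these by reference to Table 7: "Vital sign values will be considered PCI if they meet the criteria listed in" that table. No age or weight stratum is given.

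The relevant rows of Table 7 are:

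- "Systolic blood pressure (supine or sitting"): high if "≥180 And Increase of ≥20"; low if "≤90 And Decrease of ≥20".
- "Diastolic blood pressure (supine or sitting"): high if "≥105 And Increase of ≥15"; low if the value is 50 or less and has fallen by at least 15.

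The population includes children. SAP Section 8 summarizes "age group (5-10 years old, 11-15 years old, and" 16 or older.

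Other parts of the SAP also report blood pressure. Section 14.4 summarizes observed values and changes from Baseline at each visit, and Section 5.1 includes the minimum and maximum in such summaries. Section 5.5.2 puts all assessments in the listings. Section 14 presents safety summaries by antecedent treatment group and overall, not by age. Protocol Section 9.5.4 leaves subgroup details to the SAP, which specifies no subgroup analysis.

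**The concern.** A two-part rule joined by *And* is only as sensitive as its stricter part. On the high side the stricter part is a fixed limit of 180 or 105 mmHg, applied from age 5 upwards. If children start from low pressures, the fixed limit decides everything and the change criterion adds nothing. A zero or near-zero rate of high blood pressure PCI in subjects aged 5-15 could then be taken as reassurance, when the rule had little chance of registering a rise. The row belongs to a primary safety endpoint, and no other planned output counts subjects with a large rise.

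**Working it through.** **Inputs.** The limits and change criteria come from SAP Table 7. The documents give no blood pressure data, so all baseline pressures below are assumptions, shown over a range. The plan states no figure of its own to reproduce on this point.

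**Step 1: smallest rise that is counted.** Both parts must hold, so:

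- systolic: max(20, 180 − baseline)
- diastolic: max(15, 105 − baseline)

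The fixed limit alone decides whenever 180 − baseline ≥ 20, that is, at a baseline of 160 or less. For diastolic the condition is 105 − baseline ≥ 15, a baseline of 90 or less. This step needs no outside data.

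| Systolic baseline | Smallest rise counted | Diastolic baseline | Smallest rise counted |
|---|---|---|---|
| 85 | 95 | 50 | 55 |
| 100 | 80 | 60 | 45 |
| 110 | 70 | 70 | 35 |
| 120 | 60 | 75 | 30 |
| 160 | 20 | 90 | 15 |

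From 100/60 the rises needed are 80 and 45 mmHg, which are 80/20 = 4 times and 45/15 = 3 times the table's own change criteria. A systolic change from 100 to 175 is not counted; 100 to 180 is.

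**Step 2: the low side, for contrast.** The smallest fall counted is max(20, baseline − 90) systolic and max(15, baseline − 50) diastolic. A 20 mmHg systolic fall is counted at any baseline of 110 or less (110 to 90), and a 15 mmHg diastolic fall at any baseline of 65 or less (65 to 50). The problem is therefore confined to rises.

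**Step 3: how many combinations are counted.** Using whole-number steps:

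- Systolic baselines 85-120 with rises of 20-60: 36 × 41 = 1,476 combinations. One is counted (120 to 180).
- Diastolic baselines 50-75 with rises of 15-40: 26 × 26 = 676 combinations. 66 are counted, none of them with a rise below 30.

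These are counts of grid points, not expected patient rates. They show that the systolic row is the more restrictive.

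**Step 4: sensitivity to a real shift.** Assume a systolic mean of 95-115 and SD of 8-12 in children, and suppose every child's pressure rose by 30 mmHg. In the corner most favourable to the rule the mean becomes 115 + 30 = 145, and z = (180 − 145)/12 = 2.92, so at most about 0.2% of readings are counted. With mean 105 + 30 = 135 and SD 10, z = 4.5, or about 3 per million.

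**Step 5: the noise cost of counting the change alone.** Assume a within-child correlation of 0.5. The SD of a change is SD × √(2 × (1 − 0.5)) = SD. With no drug effect, the share of subjects above the criterion per visit is:

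- systolic, 20/8 = 2.50 to 20/12 = 1.67: about 0.6% to 4.8%
- diastolic (SD 8-10), 15/8 = 1.88 to 15/10 = 1.50: about 3.0% to 6.7%

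Over four post-Baseline visits the share with at least one flag is higher, at most four times the per-visit figure.

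**The case against.** The strongest reply is that the data are reported elsewhere. A large rise selected for a visit shows up in that visit's maximum change. Every reading is listed. A rise the investigator considers untoward can be recorded as an adverse event under Protocol Section 7.1.1 and counted as treatment-emergent, which is also a primary endpoint. The study is descriptive with no hypothesis testing, so no formal decision rests on an empty PCI cell. All of this stands, and it limits the point to a missing count. It does not remove it: a maximum shows one subject, not how many, and the summaries pool children with adults.

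A reader might infer that a large rise in a child is never counted, or that the rows are empty by construction. The documents do not support that. Table 7 applies at every age, so a change from 100 to 180 systolic or from 70 to 105 diastolic is counted.

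A reader might also take the very small chance that an unaffected child reads 180 or more as a measure of what is missed. It is a false-flag rate, which any outlier rule should keep low, and says nothing about missed rises.

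Finally, a change-only rule is noisy, and the documents name no pediatric blood pressure reference. Both objections are fair. They argue for an added display rather than for redefining PCI or replacing the limits.

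**Conclusion.** The point holds as a minor improvement to the SAP. Table 7's high-side change criteria have no effect at baselines of 160/90 or below, and this follows from the table alone. Higher baselines should be uncommon, because Protocol Section 4.2 excludes clinically significant vital sign abnormalities at Baseline. The further conclusion, that the high-side rows are likely to be nearly empty and uninformative at ages 5-15, rests on assumed pressures. At 100/60, rises below 80 systolic or 45 diastolic go uncounted. The conclusion is firmer for systolic than for diastolic pressure. The documents do not give the share of subjects under 16, so the number affected cannot be stated. Nothing here shows that a safety signal would be hidden from all output, nor which pressure in a child ought to be regarded as clinically important.

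**What to change.** Leave the existing Table 7 rows as they are. Add two supplementary rows giving the number and percentage of subjects with a rise from Baseline of at least 20 mmHg systolic, and of at least 15 mmHg diastolic, regardless of the observed value. Report them by visit and overall post-Baseline, by the age groups in SAP Section 8 (5-10, 11-15, 16 and older). The SAP already works this way elsewhere: Table 8 has separate rows for QTc change, and Table 7 flags weight on change alone. The thresholds are the SAP's own, so no new limit has to be chosen.

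The cost is SAP wording and a few table rows from data already collected. The drawback is extra flags from measurement noise and agitation, at about the per-visit rates in Step 5, and from growth over up to 32 months, which those rates do not include. The rows should therefore be labelled supplementary and read beside the original criteria.
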